11.2 Synthesis

The available data show that ertugliflozin decreases HbA1c, blood pressure and body weight in patients with T2D and increases incidence of urinary tract infections. This adverse effect led in rare instances to treatment discontinuation and is manageable with standard antimicrobial treatment.

APPENDIX A – Lab samples/visit – ERADICATE-HF

Sample Analysis performed at UHN

BLOOD:

Visit 1	Visit 2	Visit 3	Visit 4	Visit 5	Visit 6	Visit 7	Visit 8	Visit 9
-14	-7	0	7	14-17	42	77	84	91
Scree	Screening		Start of		Dosing		Post Visit	Follow Up
			Drug/placebo				2	
Sodium		Sodium	Sodium	Sodium	Sodium		Sodium	Sodium
Potassium		Potassium	Potassium	Potassium	Potassium		Potassium	Potassium
Urea		Urea	Urea	Urea	Urea		Urea	Urea
Creatinine		Creatinine	Creatinine	Creatinine	Creatinine		Creatinine	Creatinine
CBC & Diff		CBC & Diff	CBC & Diff	CBC & Diff	CBC & Diff		CBC & Diff	CBC & Diff
AST		AST		AST	AST			AST
ALT		ALT		ALT	ALT			ALT
Total		Total Bilirubin	Total Bilirubin	Total	Total		Total	Total
Bilirubin				Bilirubin	Bilirubin		Bilirubin	Bilirubin
Phosphate		Phosphate	Phosphate	Phosphate	Phosphate		Phosphate	Phosphate
Calcium		Calcium	Calcium	Calcium	Calcium		Calcium	Calcium
BNP		BNP	BNP	BNP	BNP		BNP	BNP
HbA1c		HbA1c		HbA1c	HbA1c			HbA1c
Glucose		Glucose	Glucose	Glucose	Glucose		Glucose	Glucose
Total		Total Protein	Total protein	Total	Total		Total	Total
Protein				Protein	Protein		protein	Protein
Lipid Profile		Lipid Profile	Lipid Profile	Lipid Profile	Lipid Profile		Lipid	Lipid Profile
							Profile	
Bicarbonate		Bicarbonate		Bicarbonate	Bicarbonate			Bicarbonate
Chloride		Chloride		Chloride	Chloride			Chloride
beta hCG								

URINE Analysis at UHN: (24 hour urine)

Visit 1	Visit 2	Visit 3	Visit 4	Visit 5	Visit 6	Visit 7	Visit 8	Visit 9
-14	-7	0	7	14-17	42	77	84	91
Screening		Baseline	Start of Drug/placebo		Dosing		Post Visit 2	Follow Up
		Sodium	Sodium				Sodium	
		Potassium	Potassium				Potassium	
	Urea		Urea				Urea	
		Creatinine	Creatinine			Creatinine		
		Albumin	Albumin			Albumin		
		Protein	Protein			Protein		

Spot Urine (done at each visit)

Visit 1	Visit 2	Visit 3	Visit 4	Visit 5	Visit 6	Visit 7	Visit 8	Visit 9
-14	-7	0	7	14-17	42	77	84	91
Screening		Baseline	Start of Drug/placebo		Dosing		Post Visit 2	Follow Up
Sodium		Sodium	Sodium	Sodium	Sodium		Sodium	Sodium
Potassium		Potassium	Potassium	Potassium	Potassium		Potassium	Potassium
Urea		Urea	Urea	Urea Urea		Urea	Urea	
Creatinine		Creatinine	Creatinine	Creatinine	Creatinine		Creatinine	Creatinine
Albumin		Albumin	Albumin	Albumin	Albumin		Albumin	Albumin
Protein		Protein	Protein	Protein	Protein		Protein	Protein

ERtugliflozin triAl in DIabetes with preserved or reduced ejeCtion FrAcTion mEchanistic evaluation in Heart Failure: "ERADICATE-HF"

Clinicaltrialgov: NCT03416270

Principal investigator(s):

[name] Division of Nephrology University Health Network, University of Toronto Toronto [contact] E-mail: [contact]

[name] Department of Clinical Pharmacology University Medical Center Groningen Groningen [contact] E-mail: [contact]

Sponsor: University Health Network Toronto, Ontario, Canada

Subsidising party: Merck (investigator initiated study)

Objectives

1. Primary objective:

The primary objective is to determine if acute and chronic ertugliflozin use causes a persistent proximal renal tubular natriuretic effect compared to placebo. Acute means changes from baseline to Visit 4 (1 week), and chronic means changes from baseline to Visit 8 (12 weeks).

2. Secondary objectives:

- 2.1. We will assess whether the proximal renal tubular natriuretic effect of ertugliflozin leads to volume contraction compared to placebo. To this end, we will determine the association between acute and chronic changes to fractional sodium handling and acute and chronic changes in volume.
- 2.2. We will assess whether volume contraction with ertugliflozin leads to a decline in hormones that are activated in heart failure (HF) patients, without activating the sympathetic nervous system (SNS) compared to placebo. To this end, we will determine the association between acute and chronic changes to volume and acute and chronic changes in hormone levels.
- 2.3. We will determine the impact of ertugliflozin on renal function. Specifically, the acute and chronic change in markers of renal hemodynamic function will be measured and compared between ertugliflozin and placebo.
- 2.4. We will determine if ertugliflozin causes a blood pressure lowering effect. Specifically, we will evaluate the acute and chronic change in cardiovascular hemodynamic assessments with ertugliflozin compared to placebo.
- 2.5. We will assess the acute and chronic changes to SNS activation with ertugliflozin use compared to placebo.
- 2.6. We will assess the acute and chronic effects of ertugliflozin on the level of urinary natriuretic modulators normalized to creatinine compared to placebo.
- 2.7. We will characterize the safety of ertugliflozin use compared to placebo.

3. Exploratory objectives:

- 3.1. We will assess whether ertugliflozin causes acute and chronic changes in measures of system volume compared to placebo.
- 3.2. We will assess whether ertugliflozin causes acute and chronic changes in measures of systemic water and fluid balance compared to placebo.
- 3.3. We will assess the acute and chronic change of all blood and urine biomarker levels with ertugliflozin compared to placebo.
- 3.4. We will determine whether changes in neurohormones are associated with changes in renal function. To this end, we will determine the association between acute and chronic changes in absolute measures of renal function and the acute and chronic changes in neurohormones with ertugliflozin compared to placebo.

- 3.5. We will determine whether changes in neuro-hemodynamic markers associated with HF patients are associated with changes in arterial stiffness. To this end, we will determine the association between acute and chronic changes in arterial stiffness and the corresponding acute and chronic changes in neuro-hemodynamic markers with ertugliflozin compared to placebo.
- 3.6. We will determine whether changes in neurohormones that are activated in HF patients are associated with changes in blood pressure. To this end, we will determine the association between acute and chronic changes in blood pressure and the acute chronic changes in neurohormones with ertugliflozin compared to placebo.
- 3.7. We will assess the acute and chronic effects of ertugliflozin on the level of oxidative stress markers compared to placebo.
- 3.8. We will assess the acute and chronic changes with ertugliflozin on urine and plasma chemistry marker levels and metabolic parameters compared to placebo.

Outcomes

1. Outcomes for the primary objective:

- 1.1. The primary outcome is measured by the acute and chronic change in lithium clearance from baseline with ertugliflozin vs placebo. $FE(Li^+) = 100 X ([(urine Li^+) X (creatinine plasma)]/[(plasma Li^+) X (creatinine urine)]$
- 1.2. We will also measure the primary objective on these secondary outcomes:a. *Total overall (proximal and distal) tubular sodium handling*
 - $FE(Na^+) = 100 X ([(urine Na^+) X (creatinine plasma)]/[(plasma Na^+) X (creatinine urine)]$ b. Distal sodium handling: $FE(Na^+) - FE(Li^+)$

2. Outcomes for the secondary objectives:

- 2.1. Relationship between proximal renal tubular natriuretic effects and volume reduction: proximal renal tubular natriuretic effects will be evaluated by lithium clearance FE(Li+); volume change will be measured using the following two outcomes:
 - a. Plasma volume (PV)
 - *i.* Measured by indocyanine green (for site 2 and 3)
 - ii. Estimated percent change by Strauss estimation
 - $([{Hb_{baseline}/Hb_{end}} \times {(100-Ht_{end})/(100-Ht_{baseline})}]-1) \times 100$
 - b. Extracellular fluid (ECF)
 - *i.* Measured by bioimpedance spectroscopy
- 2.2. Relationship between volume and hormones: Volume will be measured by PV and ECF. Hormones will be measured by:
 - a. Hormones activated in HF patients (NT-proANP, BNP)
 - b. Renin-angiotensin-aldosterone system (RAAS) markers (serum aldosterone, renin, PRA, ANGII, AGT, ACE2, ACE)

- c. SNS markers (norepinephrine, epinephrine, heart rate, heart rate variability (SDNN and RMSSD)
- 2.3. Renal hemodynamic function will be measured using the following groups of outcomes:
 - a. Absolute measured values
 - i. mGFR
 - *ii.* ERPF (for site 1 and 2)
 - iii. Hematocrit
 - b. Creatinine-derived values
 - *i.* 24-hour Crt (mmol/day)
 - *ii. Creatinine clearance (ml/min)*
 - c. Gomez-derived values (for site 1 and 2)
 - *i.* RBF = RPF/(1-HCT)
 - *ii.* RVR = MAP/RBF [Mean arterial pressure = MAP]
 - *iii. Filtration fraction* = *GFR/RPF*
 - iv. $PGLO = (GFR/KFG) + 10mmHg + [5 \times (TP/FF \times ln(1/1-FF)-2)]$
 - v. $R_A = [(MAP PGLO)/RBF] \times 1,328$
 - vi. $R_E = [GFR/(KFG \times (RBF-GFR))] \times 1,328$
- 2.4. Blood-pressure lowering effect will be measured using the following group of outcomes:
 - a. blood pressure (systolic [SBP] and diastolic [DBP])
 - b. NICOM parameters
 - c. echocardiographic measures
 - d. systemic vascular resistance
 - e. arterial stiffness
 - *i.* radial, aortic and carotid augmentation index (AIx)
 - *ii.* carotid-radial pulse-wave velocity (PWV)
 - iii. carotid-femoral PWV
- 2.5. SNS activation will be measured by norepinephrine, epinephrine, heart rate and heart rate variability (RMSSD and SDNN).
- 2.6. Changes to urinary natriuretic modulators will be assessed by the level of ACE-2, adenosine, ACE activity, NT-proANP and ANGII, normalized to urine creatinine.
- 2.7. Safety will be assessed by the number of hypoglycemic episodes and serious adverse events.

3. Outcomes for the exploratory objectives:

- 3.1. Volume contraction will be assessed by:
 - a. Plasma volume measured by ICG (site 2 and 3)
 - b. Plasma volume measured by Strauss estimation
 - c. Extracellular body of water measured by bioimpedance spectroscopy
- 3.2. Water and fluid levels will be assessed by:
 - a. Absolute (L) and relative (%) total body water (TBW)
 - b. Absolute (L) and relative (%) intracellular fluid (ICF)
 - c. Absolute (kg) and relative (%) fat-free mass (FFM)
 - d. Absolute (kg) and relative (%) fat mass (FM)
 - e. BMI

- 3.3. The blood and urine biomarkers are:
 - a. Blood: Hemoglobin, hematocrit, creatinine, total bilirubin, albumin, bicarbonate, NT-proANP, BNP, PGF2a, cGMP, nitric oxide (nitrite, nitrate, total nitrite)
 - b. Urine: NT-proANP, sodium, RAAS markers normalized to urine creatinine
 - *i.* 24-hour urine clearance markers (protein, creatinine, UACR, urea, potassium, sodium)
- 3.4. Relationship between neurohormones and renal function. Hormones will be measured by NT-proANP, BNP, and RAAS markers (serum aldosterone, renin, PRA, ANGII, AGT, ACE2, ACE). Absolute measure of renal function outcomes is measured by:
 - a. mGFR
 - b. ERPF
 - c. hematocrit
- 3.5. Relationship between arterial stiffness and neuro-hemodynamic markers. Markers will be measured by SBP, DBP, MAP, NT-proANP, BNP, SNS markers (epinephrine, norepinephrine) and RAAS markers (serum aldosterone, renin, PRA, ANGII, AGT,
 - ACE2, ACE). Arterial stiffness outcomes will be measured by:
 - a. Radial, aortic and carotid AIx
 - b. Carotid-radial PWV
 - c. Carotid-femoral PWV
- 3.6. Relationship between neurohormones and blood pressure. Hormones will be measured by NT-proANP, BNP, and RAAS markers (serum aldosterone, renin, PRA, ANGII, AGT, ACE2, ACE). SBP, DBP, and MAP will be the outcome.
- 3.7. Urine oxidative stress markers normalized to urine creatinine, including 8-isoprostane, 8-OHdG, cGMP, nitric oxide (endogenous nitrite, nitrate, total nitrite), PGF2a, as well as plasma oxidative stress markers, such as cGMP, nitric oxide, and PGF2a.
- 3.8. Plasma/urine chemistry markers and metabolic parameters are:
 - a. Metabolic (weight, waist measurement, HbA1c)
 - b. Urine chemistry (UACR, urea, protein, potassium)
 - c. Plasma chemistry:
 - i. Sodium, potassium, urea, urate, magnesium, phosphate, chloride, calcium
 - *ii.* AST, ALT, ALP, LDL, HDL, cholesterol, triglyceride
 - *iii. Glucose, total protein*

Statistical Analysis Plan (SAP)

- 0. Summary of baseline demographic and clinical characteristics separated by ertugliflozin group and placebo group will be generated. Significance testing between-group will be performed. The following variables will be included:
 - *Age, sex, weight, waist circumference, BMI, HbA1c, hemoglobin, fasting blood glucose*
 - race (white/black/Hispanic/Asian/other)
 - SBP, DBP, HR
 - Mean eGFR
 - UACR (median and IQR)
 - Concomitant medication (ACEi, ARB, Diuretic, statin)

1. Analysis for the primary objective:

- 1.1. To assess ertugliflozin-related acute and chronic changes in the primary outcome FE(Li+) compared to placebo, linear mixed-effects models will be used. Two separate models will be fit. For acute change, the vector of outcomes will include the baseline and 1-week values (i.e. Visit 3 and Visit 4 values). For chronic changes, the vector of outcomes will include the baseline and 12-week values (i.e. Visit 3 and Visit 8 values). The covariates will include the visit and treatment-by-visit interaction; due to randomization, a covariate for the main effect of treatment will not be included. The treatment-by-time coefficient, its 95% confidence interval, and its p-value will be used to assess the effect of treatment.
- 1.2. We will repeat this analysis with:
 - a. FE(Na+) as an outcome
 - b. FE(Na+) FE(Li+) as an outcome
- 1.3. In exploratory analysis to determine the overall effect of ertugliflozin across all timepoints, we will repeat the above analysis with one model where the vector of outcomes will include all data collected at baseline, 1-week, and 12-week values.

2. Analysis for secondary objective:

- 2.1. Linear regression will be performed with change in volume as the dependent variable and change in FE(Li+) as the independent variable, with treatment as a covariate. Two separate models will be fit for acute and chronic changes. Acute changes will use the baseline and 1-week values for both the dependent and independent variable values; chronic changes will use baseline and 12-week values.
- 2.2. The same models described in the analysis of secondary objective 2.1 will be completed, with changes in PV or ECF as independent predictors, for neurohormones as the dependent variables/outcomes.
- 2.3. 2.6. The same models described in the analysis of primary objective 1.1 and 1.3 will be completed for each of the different outcomes.
- 2.7.The numbers of hypoglycemic events and serious adverse events will be reported for both the placebo group and ertugliflozin group. No statistical comparisons will be performed.

3. Analysis for exploratory objective:

- 3.1.– 3.3. The same models described in the analysis of primary objective 1.1 and 1.3 will be performed for each of the different outcomes.
- 3.4. The same models described in the analysis of secondary objective 2.1 will be completed, with changes in neurohormones as independent predictors, for changes in absolute measure of renal function as the dependent variables/outcomes.
- 3.5. The same models described in the analysis of secondary objective 2.1 will be completed, with changes in neuro-hemodynamic markers as independent predictors and changes in arterial stiffness as the different dependent variables/outcomes.

- 3.6. The same models described in the analysis of secondary objective 2.1 will be completed, with changes in neurohormones as independent predictors and changes to blood pressure as dependent variable/outcome.
- 3.7.– 3.8. The same models described in the analysis of primary objective 1.1 and 1.3 will be completed for each of the different outcomes.

Analysis population: The intention to treat population will be used for all analyses. There are no planned subgroup analyses for the primary outcome.

Hypothesis testing: For hypothesis testing, a 5% significance level will be used (two-sided). No interim analyses will be performed. For secondary objectives, nominal p-values will be reported.

General model assumptions and model diagnostic procedures: For the linear mixed-effects models with visit and treatment-by-visit interaction as covariates, a participant-level random intercept will be included. Restricted-maximum-likelihood will be used for estimation and the missing-at-random framework will be assumed. Plots of marginal and conditional residuals will be used for model diagnostics and assessment. Similar diagnostic procedures will be used for the linear regression models.

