3. STUDY POPULATION

Version number: 6.0 23-APR-2020

Population (base)

The study population will be selected from the outpatient clinics from hospitals based in the Netherlands (Groningen) and Canada (Toronto).

Inclusion criteria:

- 1. Male or female subjects diagnosed with T2D \geq 12 months prior to informed consent;
- 2. eGFR \geq 30 ml/min/1.73m²;
- 3. Age >18 years;
- 4. HbA1c 6.5%-10.5%;
- 5. Body Mass Index (BMI) 18.5-45.0 kg/m²;
- 6. Blood pressure $\leq 160/110$ and $\geq 90/60$ at screening,
- Heart failure with New York Heart Association (NYHA) class 2-3 symptoms and ejection fraction ≥20%
- 8. Stable dose of maximally tolerated ACE inhibitor, angiotensin receptor blocker or renin inhibitor for at least 30 days
- 9. Stable diuretic dose for at least 30 days at the time of baseline physiological assessment
- 10. BNP levels at baseline \geq 100 pg/ml (no atrial fibrillation), \geq 200 pg/ml if in atrial fibrillation

Exclusion criteria:

- 1. Type 1 Diabetes;
- 2. Leukocyte and/or nitrite positive urinalysis that is untreated;
- 3. Severe hypoglycaemia within 2 months prior to screening;
- 4. History of brittle diabetes or hypoglycaemia unawareness based on investigator judgement;
- 5. Unstable coronary artery disease with acute coronary syndrome, percutaneous intervention or bypass surgery within 3 months;
- 6. Clinically significant valvular disease;
- 7. Congestive heart failure secondary to an infiltrative cardiomyopathic process (for example amyloid) or pericardial constriction;
- 8. Uncontrolled systemic hypertension (systolic blood pressure >160 mmHg and/or diastolic blood pressure >110) or systemic hypotension (systolic blood pressure < 90/60 mmHg);
- 9. Bariatric surgery or other surgeries that induce chronic malabsorption;
- 10. Anti-obesity drugs or diet regimen and unstable body weight three months prior to screening;
- 11. Treatment with systemic corticosteroids;
- 12. Blood dyscrasias or any disorders causing hemolysis or unstable red blood cells;
- 13. Pre-menopausal women who are nursing, pregnant, or of child-bearing potential and not practicing an acceptable method of birth control;
- 14. Participation in another trial with an investigational drug within 30 days of informed consent;

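### As printed, the logarithm in the SAP's glomerular pressure formula evaluates to ln(1-FF), which reverses the protein term, lowers PGLO and inflates R_A; one bracket corrects it

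*SAP*

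**What the plan says.** SAP Outcomes 2.3.c lists derived renal haemodynamic outcomes for sites 1 and 2. Item iv is "PGLO = (GFR/KFG) + 10mmHg + [5 \times (TP/FF \times ln(1/1-FF)-2", followed by closing brackets. Item v uses that result: "R_A = [(MAP PGLO)/RBF] \times 1,328". No operator is visible between MAP and PGLO in the text available here; I read it as a minus sign. Item vi, "R_E = [GFR/(KFG \times (RBF-GFR))] \times 1,328", uses neither PGLO nor the logarithm. FF is defined in the same list as GFR over RPF.

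SAP Analysis 2.3 to 2.6 sends these outcomes to the mixed models: "The same models described in the analysis of primary objective 1.1 and 1.3 will be completed for each of the different outcomes". The effect measure is therefore the treatment-by-visit coefficient.

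Total protein is measured (SAP Outcomes 3.8: "Glucose, total protein"), but TP has no unit in the formula. KFG has neither a value nor a unit in either document.

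**The concern.** The printed expression 1/1-FF equals 1-FF, so the formula takes ln(1-FF), which is negative for every FF between 0 and 1. A limit check shows which form was meant, without any outside source. As FF approaches 0, (TP/FF) x ln[1/(1-FF)] tends to TP, the protein concentration. The printed form tends to -TP, a negative concentration.

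A programmer who follows the SAP literally would get too low a PGLO and too high an R_A. The protocol's rationale describes afferent vasoconstriction and a fall in intraglomerular pressure as the expected renal mechanism, and these two derived quantities address it most directly. The error also varies with TP and FF, both of which may shift on a drug that contracts volume, so comparing arms does not remove it.

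**Working it through.** The documents give no PGLO or R_A value, so there is no figure of the plan's own to reproduce.

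**Algebra.** Let CM = (TP/FF) x ln[1/(1-FF)]. The +10 and the 5 x (-2) cancel in both forms.

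- Bracketed: PGLO = GFR/KFG + 5 x CM
- Printed: PGLO = GFR/KFG - 5 x CM
- Error: -10 x CM, whatever the value of KFG

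**Inputs.** The assumed record is GFR 75 mL/min (1.25 mL/s), RPF 400 mL/min, haematocrit 0.40 and TP 7.0 g/dL. KFG is assumed to be 0.08 to 0.1733 mL/s/mmHg. The GFR is above the entry limit, "eGFR \geq 30 ml/min/1.73m²". The MAP range comes from the eligibility criterion "Blood pressure $\leq 160/110$ and $\geq 90/60$ at screening": (90 + 2 x 60)/3 = 70 and (160 + 2 x 110)/3 = 126.7 mmHg. The central value is assumed to be 90.

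**PGLO.** FF = 75/400 = 0.1875 and ln[1/(1-0.1875)] = 0.2076, so CM = (7.0/0.1875) x 0.2076 = 7.75. The term 5 x (CM - 2) is +28.8 mmHg; as printed it is 5 x (-CM - 2) = -48.8 mmHg. The error is -77.5 mmHg.

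| KFG | GFR/KFG | PGLO bracketed | PGLO printed |
|---|---|---|---|
| 0.08 | 15.6 | +54.4 | -23.1 |
| 0.1733 | 7.2 | +46.0 | -31.5 |

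**R_A.** RBF and 1,328 cancel in the ratio of printed to bracketed, which is 1 + 10 x CM/(MAP - bracketed PGLO).

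| MAP (mmHg) | Ratio at KFG 0.08 | Ratio at KFG 0.1733 |
|---|---|---|
| 70 | 1 + 77.5/15.6 = 6.0 | 1 + 77.5/24.0 = 4.2 |
| 90 | 1 + 77.5/35.6 = 3.2 | 1 + 77.5/44.0 = 2.8 |
| 126.7 | 1 + 77.5/72.3 = 2.1 | 1 + 77.5/80.7 = 2.0 |

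**Sign of PGLO.** Printed PGLO is negative only if GFR/KFG is below 5 x CM. On an assumed grid (GFR 30 to 120 mL/min, FF 0.15 to 0.30, TP 6 to 8 g/dL), 100% of points are negative at KFG 0.0867 to 0.12, 99% at 0.06 and 73% at 0.04.

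**Change from baseline.** The error in a patient's change is -10 x (change in CM). If CM does not change on placebo, this is approximately the error in the treatment-by-visit coefficient. Two assumed on-drug patterns, with results given for KFG 0.08 to 0.1733:

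| Pattern | CM | Change, bracketed (mmHg) | Change, printed (mmHg) | Error |
|---|---|---|---|---|
| GFR 75 to 70, RPF 400, TP 7.0 to 7.1 | 7.752 to 7.805 | -0.78 to -0.22 | -1.31 to -0.75 | -0.53 |
| GFR 45 to 42, RPF 280, TP constant at 7.0 | 7.631 to 7.584 | -0.86 to -0.52 | -0.39 to -0.05 | +0.47 |

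The fall is overstated when TP rises and understated when TP is constant.

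**The case against.** The best defence is that this is a typing slip that never reaches the analysis. The intended form is recognisable, negative glomerular pressures would stand out at first output, and nothing shows that any code follows the printed string. The SAP sets its equations loosely: the FE(Li+) and FE(Na+) formulas each lack a closing bracket. A bracket lost in reading the PDF cannot be excluded either, though the brackets in the RBF and R_E formulas survive. Protocol 6.1.2 refers the derived renal parameters to a published description, and Protocol 6.3 refers the renal tests to a laboratory manual, so KFG and the units may be fixed there. All of this stands and lowers the severity. It does not make the printed rule correct, and the SAP cites no source beside the formula.

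Four stronger readings are tempting, but the documents do not support them.

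- **Every patient would have a negative PGLO.** That needs a KFG value, which is not given. At an assumed 0.04 about a quarter of the grid stays positive.
- **R_A would be wrong by a constant factor of three.** Three is a mid-range value near MAP 90; the factor varies with MAP and KFG.
- **Flows would enter in mL/min and make R_A 60 times too small.** Among the 2.3 outcomes, that unit is attached only to creatinine clearance, which is not an input to these equations.
- **Objective 2.3 rests on PGLO and R_A.** It lists eleven outcomes, and nine are untouched: mGFR, ERPF, haematocrit, 24-hour creatinine, creatinine clearance, RBF, RVR, FF and R_E. Vasoconstriction can also be read from RVR, RBF and R_E.

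The large level error also shrinks in the contrast that is analysed, from 77.5 mmHg to about 0.5 mmHg in these examples. Quoting that error as a multiple of the true change would mislead, because the true changes are themselves close to zero.

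**Conclusion.** The point holds, as a minor one. The printed formula evaluates to ln(1-FF) and lowers PGLO by exactly 10 x (TP/FF) x ln[1/(1-FF)] in every record at sites 1 and 2. That part is algebra and needs no KFG. The sizes rest on assumed inputs: for the record above, a PGLO of -23 to -32 mmHg instead of +54 to +46 mmHg, an R_A about 2 to 6 times too high across eligible MAP, and an error of about 0.5 mmHg in the PGLO change. Neither the sign of PGLO in a given patient nor the direction of the error in the arm difference can be fixed from the documents.

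Only two secondary outcomes are affected, their p-values are nominal, and the primary outcome FE(Li+) is untouched. A reader should not infer that the analysis has been or will be run with the wrong sign; the documents show only that the written rule is wrong.

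**What to change.** In SAP Outcomes 2.3.c.iv, write PGLO = GFR/KFG + 10 + 5 x {(TP/FF) x ln[1/(1-FF)] - 2}. Add a programming check that 0 < PGLO < MAP for each record before R_A is computed. With the record above, the check would catch the printed form.

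As supporting documentation, state beside the formulas the KFG value and unit, and the units of GFR, RPF, TP and HCT. The haematocrit scale needs stating because the plasma volume formula in SAP Outcomes 2.1 uses percent, whereas RBF in 2.3.c uses a fraction.

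The cost is one bracket, one line of units and one check in the code. No new data, patients or procedures are needed. If the code already uses the bracketed form, only the text changes.

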2. STUDY DESIGN

This study will use a double blind, stratified randomization trial approach involving 36 T2D-HF patients taking standard HF therapies, who will be allocated to either ertugliflozin or placebo in a 1:1 ratio (Table 1 – inclusion and exclusion criteria). For feasibility, participants will be recruited from the >4000 HF patients followed at UHN-MSH heart failure clinics and from heart failure clinics in Groningen, the Netherlands, of whom >40% have T2D. The study will consist of a screening visit, a 4-week run-in phase for those subjects not on stable ACEi/ARB treatment, followed by a 12-week double blind treatment period.

The target population will be invited for screening. Subjects who meet all entry criteria and who are already on a stable dose (no changes in dose or type of drug) of ACEis or ARBs for at least 4 weeks proceed directly to randomization. Subjects who had their ACEi or ARB medication changed during the preceding 4 weeks of the screening visit proceed to a run-in phase during which the type and dose of these drugs are stabilized. Subjects will be randomly assigned to one of the two treatments. Subjects will have their study visit in the morning in fasted condition.

Subjects will be instructed to take the study medication once daily, in the morning, except on study days; on those days, the study drug will be taken after the patient visit.

Measurements:

- During the double blind treatment period, patients will collect a 24-hour urine collection at each visit for measurement of 24-hour protein, albumin, glucose, sodium, potassium, creatinine, and urea excretion. Twenty-four hour urine collections will be performed at: Visits 3, 4 and 8. Routine biochemistry and safety labs will be drawn at screening, during each physiological assessment and at each the specified office safety visits (see visit schedule table below).
- Office systolic and diastolic blood pressure measurements, heart rate, weight, and waist circumference will be performed at screening and at each subsequent physiological testing day and at each office visit (see visit schedule table below).
- Blood will be drawn for measurement of renal function tests, HbA1c, glucose, complete blood count, plasma albumin, RAAS biomarkers, natriuretic peptides, and neurohormones on visits 3, 4 and 8.
- Blood and urine samples will be stored for future exploratory biomarker analyses to study the effect of ertugliflozin in this study population.

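### Appendix A leaves HbA1c, AST, ALT, bicarbonate and chloride blank at Visits 4 and 8, the only follow-up visits the SAP models for these exploratory outcomes

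*SAP*

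**What the plan says.** **SAP, time points.** The primary objective fixes the visits: "Acute means changes from baseline to Visit 4 (1 week), and chronic means changes from baseline to Visit 8 (12 weeks". Analysis 1.1 fits one mixed model to Visits 3 and 4 and another to Visits 3 and 8. Analysis 1.3 pools these visits and adds no others: "the vector of outcomes will include all data collected at baseline, 1-week, and 12-week values".

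**SAP, outcomes.** Outcome 3.8 names HbA1c in "Metabolic (weight, waist measurement, HbA1c", chloride in "Sodium, potassium, urea, urate, magnesium, phosphate, chloride, calcium", and AST and ALT in "AST, ALT, ALP, LDL, HDL, cholesterol, triglyceride". Outcome 3.3 names bicarbonate among the blood biomarkers. For 3.7 to 3.8 the analysis section states: "The same models described in the analysis of primary objective 1.1 and 1.3 will be completed for each of the different outcomes". The entry for 3.1 to 3.3 says the same in substance.

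**Protocol section 2, Measurements.** Blood is to be drawn for a list that includes "HbA1c, glucose, complete blood count, plasma albumin, RAAS biomarkers, natriuretic peptides, and neurohormones on visits 3, 4 and 8". The same list of measurements provides for routine biochemistry and safety labs at screening, at each physiological assessment and at the office safety visits, without naming the analytes.

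**Protocol Appendix A, blood table.** HbA1c, AST, ALT, bicarbonate and chloride have entries at Visits 1, 3, 5, 6 and 9. Their cells at Visits 4 and 8 are empty.

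**The concern.** Appendix A is the only table in the documents that sets individual analytes against individual visits, so a site or laboratory could well order from it. If it did, these five markers would have a baseline value but no value at either visit that the SAP models.

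Modelling cannot repair that gap. The mixed model is fitted under a missing-at-random assumption, and protocol section 8.2 provides for multiple imputation. Both need some observed values at the visit in question. With none in either arm, there is nothing from which to estimate the treatment-by-visit coefficient or to build an imputation.

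HbA1c is the most visible of the five. Protocol section 11.1(i) names it among the surrogates by which efficacy is monitored, yet under Appendix A it has no end-of-treatment value.

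**Working it through.** The plan gives no figure to reproduce here. The check sets the sampling schedule against the analysis schedule.

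**Step 1: visits and days** (schedule of procedures, protocol section 2). Visit 3 is Day 0, Visit 4 Day 7, Visit 5 Days 14-17, Visit 6 Day 42, Visit 8 Day 84 and Visit 9 Day 91. Visit 9 falls one week after study drug stops.

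**Step 2: filled cells in the Appendix A blood table.**

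| Analyte | Visits with an entry | SAP outcome |
|---|---|---|
| HbA1c | 1, 3, 5, 6, 9 | 3.8a |
| AST | 1, 3, 5, 6, 9 | 3.8c(ii) |
| ALT | 1, 3, 5, 6, 9 | 3.8c(ii) |
| Bicarbonate | 1, 3, 5, 6, 9 | 3.3a |
| Chloride | 1, 3, 5, 6, 9 | 3.8c(i) |
| Sodium (for comparison) | 1, 3, 4, 5, 6, 8, 9 | 3.8c(i) |

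A damaged table is an unlikely explanation. Five rows share one pattern, while sodium, phosphate, calcium, BNP and glucose in the same table are filled at Visits 4 and 8.

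**Step 3: overlap with the SAP.** The modelled follow-up visits are {4, 8}. For the five analytes, {1, 3, 5, 6, 9} and {4, 8} have no element in common; only the baseline, Visit 3, is shared. Every available record would then be a baseline record, so neither the visit effect nor the treatment-by-visit effect in analysis 1.1 is estimable. The model in 1.3 fails for the same reason.

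**Step 4: number of comparisons affected, by reading of the protocol.**

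- Appendix A governs: 5 markers x 2 time points = 10.
- Section 2 governs, and its routine labs exclude the four markers it does not name: HbA1c is recovered, leaving 4 x 2 = 8.
- Section 2 governs, and its routine labs include those four: 0.

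**Step 5: gap in on-drug data under Appendix A.** The last on-drug value is at Visit 6, Day 42. The next scheduled value is at Day 91, off drug. The stretch of treatment without a value is 84 - 42 = 42 days, half of the 84-day schedule.

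**The case against.** The strongest reply is that a blank in Appendix A does not show that no sample is taken. Several facts support it.

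- Section 2 schedules HbA1c explicitly at Visits 3, 4 and 8, and places routine biochemistry at each physiological assessment.
- The schedule of procedures marks blood and urine samples at Visits 4 and 8. Section 6.3 takes about 20 ml for routine tests at each of 7 visits, which matches the seven visits so marked (1, 3, 4, 5, 6, 8 and 9).
- Appendix A is not exhaustive. It has no row for lithium, on which the primary outcome depends, and none for plasma albumin, alkaline phosphatase, urate or magnesium.
- Appendix A is headed as analysis at one centre, whereas section 6.3 assigns routine measurements to the local laboratories.
- Serum and plasma are stored, and electrolytes are named as possible later assays, so chloride might be recoverable.

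These points have force. A reader might infer that the analyses cannot be run, or that ten comparisons are certain to have no data. The documents do not support that: for HbA1c there is a contradiction within the protocol, and for the other four, availability is unclear. Nor do they support saying that glycaemia or the liver goes entirely unmeasured at 12 weeks. Appendix A keeps glucose (though under the clamp) and total bilirubin at both visits.

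The reply does not remove the problem. An analyte with no row may be handled elsewhere; an analyte with a row and two empty cells has a stated schedule. That schedule conflicts with section 2 for HbA1c and does not supply the visits the SAP needs for any of the five. The general routine-labs sentence cannot settle the other four, because it names none of them.

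**Conclusion.** The inconsistency is real. Its consequence is conditional. If Appendix A is followed, the acute and chronic treatment effects for HbA1c, AST, ALT, bicarbonate and chloride cannot be estimated: up to 10 comparisons, with no on-drug value after Day 42. The number falls to 8 or 0 under the two readings of section 2 set out above.

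The conclusion assumes that the extracted Appendix A rows are faithful, which their common pattern supports, and that the SAP means what it says about visits. It does not assume that samples were in fact missed; the documents cannot show that either way.

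A reader might also infer damage to the main results. That does not follow. All five markers are outcomes only of exploratory objectives 3.3 and 3.8. No primary or secondary analysis uses them, and the SAP's safety outcomes are hypoglycaemic episodes and serious adverse events. The point deserves correction because it is cheap to correct and because samples never taken cannot be recovered by analysis.

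**What to change.** Reconcile Appendix A, protocol section 2 and SAP 3.3/3.8.

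1. **If sampling is still under way:** add the five assays to the Visit 4 and Visit 8 columns of Appendix A, and have section 2 either name the analytes in its routine labs or refer to the appendix. Blood is already taken at both visits, so the cost is a few routine assays and a one-table amendment.
2. **If sampling is complete:** state which of these values exist at Visits 4 and 8. For any that do not, remove the marker from SAP 3.3/3.8, or specify its analysis as the change from Visit 3 to Visit 6. Do this before the data are analysed, so that no outcome is dropped or moved to another visit after results are seen. The Visit 6 option has a price: it estimates a 6-week effect (Day 42) in place of the 12-week effect, and should be labelled so.
3. **In the same edit:** confirm where plasma albumin, urate, magnesium and alkaline phosphatase are scheduled. SAP 3.3 and 3.8 analyse them, but they have no row in the Appendix A blood table.
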